4.2. Variable Definitions

The following variables will only be calculated if not reported on the eCRF.

4.2.1. Age

Subject age was collected before enrollment.

Age category 1 is defined as < 65 years and ≥ 65 years, and age category 2 is defined as < 65 years, 65 to 74 years, 75 to 84 years, and ≥ 85 years.

4.2.2. Body Mass Index

Body mass index will be calculated as follows:

$$\text{BMI (kg/m}^2\text{)} = [\text{weight (kg)}] / [\text{height (m)}]^2.$$

4.2.3. Body Surface Area

Body surface area will be calculated based on the Mosteller (1987) formula as follows:

$$\text{BSA (m}^2\text{)} = \{[\text{weight (kg)} \times \text{height (cm)}] / 3600\}^{1/2}.$$

Sites will also record the BSA calculated per institutional standards.

4.2.4. Prior and Concomitant Medication

Prior medication is defined as any nonstudy medication taken within 30 days before the first dose of study drug.

Concomitant medication is defined as any nonstudy drug that is started accordingly:

- Before the date of first administration of study drug and is ongoing throughout the study or ends on/after the date of first study drug administration.
- On/after the date of first administration of study drug and is ongoing or ends during the course of study drug.

A prior medication could also be classified as "both prior and concomitant medication" if the end date is on or after first dose of study drug.

For the purposes of analysis, all medications will be considered concomitant medications unless the medications can unequivocally be defined as not concomitant.

The start/stop dates recorded in the eCRF by the investigator and his or her research staff will be used to identify when a concomitant medication was taken during the study. Unresolved missing start dates will be handled as follows:

- For the starting date, impute as follows:
 - If the day is missing, then impute as the first day of the month.
 - If the month is missing, then impute as the first day of the year.
 - If the year is missing, then the medication will be considered both prior and concomitant.
- For the ending date, impute as follows:
 - If the day is missing, then impute as the last day of the month.
 - If the month is missing, then impute as the last day of the year.

If the year is missing, then the medication will be considered as ongoing until the end of the study.

Note that the above imputation rules are for the purpose of defining prior and concomitant medications in the study. Imputed start/end dates are not saved in the analysis dataset.

5. STATISTICAL METHODOLOGY

5.1. General Methodology

Unless otherwise noted, SAS® software (SAS Institute Inc, Cary, NC; Version 9.4 or later) will be used for the generation of all tables, graphs, and statistical analyses. Descriptive summaries for continuous variables will include, but not be limited to, the number of observations, mean, standard deviation, median, minimum, and maximum. Descriptive summaries for categorical variables will include the number and percentage of subjects in each category.

Interim analyses are planned for this study as defined in Section 9.

5.2. Treatment Groups

This is a randomized, double-blinded, placebo-controlled study with itacitinib or placebo in combination with corticosteroids. There are 2 treatment groups. Subjects will be randomized 1:1 to itacitinib 200 mg plus corticosteroids or matching placebo plus corticosteroids.

5.3. Analysis Sets

5.3.1. Interim Analysis 1

The Interim Analysis 1 clinical data cutoff date was defined as the date when the first 112 randomized and dosed subjects have either completed the Day 28 visit or withdrawn from the study. This occurred on 25 JUN 2018.

5.3.1.1. Interim 1 Analysis Set

The Interim 1 analysis set contains all subjects who have been randomized and have received at least 1 dose of study drug as of the Interim 1 cutoff date. The Interim 1 analysis set will be used for both planned efficacy and safety analyses at Interim Analysis 1. Note that subjects randomized after the 112th subject in the Interim 1 analysis set are not included in Interim 1 analyses, even though they might have safety and efficacy data in the clinical database as of the Interim 1 cutoff date. Because Interim Analysis 1 includes limited numbers of analyses, only 1 analysis set is defined, which is used for both efficacy and safety analyses.

5.3.2. Interim Analysis 2

The Interim Analysis 2 cutoff date is when the 240th eligible subject randomized in the study reaches Day 180 in the treatment phase. This occurred on 17 APR 2019.

5.3.2.1. Interim 2 Efficacy Analysis Set

The Interim 2 efficacy analysis set contains all subjects who have been randomized as of the Interim Analysis 2 clinical data cutoff date but excludes subjects who are ongoing at the clinical data cutoff date and have not finished the Day 28 visit. The Interim 2 efficacy analysis set will be used for all planned efficacy analyses at Interim Analysis 2.

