### **5.5. Withdrawal of Subjects From Study Treatment**

The decision to discontinue study treatment will not constitute study completion (see Section 5.5.3). In the event that the decision is made to discontinue study treatment, the treatment period will be considered complete, and the follow-up period will begin.

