### 9.4. Statistical Analyses

#### 9.4.1. Primary Analyses

The primary endpoint is ORR at Day 28, defined as the proportion of subjects demonstrating a CR, VGPR, or PR, as per standard criteria (Harris et al 2016, CIBMTR 2009). The comparison of ORR at Day 28 between treatment cohorts will be conducted once the last subject completes the Day 28 visit or withdraws from the study. A CMH test with normal approximation will be used. Summary statistics and 95% CI will be provided.

Subjects who are missing Day 28 aGVHD response assessment data will be considered to be nonresponders.

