Table 2: Operation Characteristics Using Hwang-Shih-DeCani Alpha Spending Function With Shape Parameter -4

		No. of Subjects (%)	Alpha Spent /Cumulative	Efficacy Boundary or Critical Value (as Compared With Observed Normalized Test Statistic z)	Nominal Significance /Alpha Level: $1 - \Phi(d)$	Efficacy Boundary or Critical Value at Chi-Square Test Statistic With Degree of Freedom 1
ORR at Day 28	Interim Analysis 1	112 (25.7)	–	–	–	–
	Interim Analysis 2	360 (82.6)	0.0122/0.0122	2.249810	0.0122305	5.061645
	Final	436 (100)	0.0128/0.025	2.015483	0.02192703	4.062172

If, at Interim Analysis 2, the observed number of subjects who have completed Day 28 is different from 360, then the boundaries for efficacy in [Table 2](#) will be recalculated using observed information fraction.

The interim analyses will be performed by an independent statistician and programmer not involved with the conduct of the study as described in the DMC charter.

At the Interim Analysis 2 clinical data cutoff date, the date when the 240th eligible subject randomized in the study has reached Day 180, 360 subjects are expected to have been randomized. Testing of Day 28 ORR will be conducted for subjects who have completed the Day 28 visit or withdrew from the study by the clinical data cutoff date. This means that subjects who were ongoing but had not yet reached the Day 28 visit by the Interim Analysis 2 clinical data cutoff date will be excluded from both the Day 28 ORR and NRM efficacy analyses.

[Figure 4](#) depicts the recommended decision process at Interim Analysis 2: first, testing Day 28 ORR using stratified CMH and assuming 360 subjects have completed Day 28 or withdrew from the study by the cutoff date, if observed normalized test statistic is ≤ 1.46 , it is recommended to stop the study for futility; if the observed normalized test statistic of Day 28 ORR is ≥ 2.25 , then the NRM rate at Day 180 will be tested using the Bonferroni method. If both the primary efficacy analysis and the key secondary efficacy analysis pass their corresponding efficacy boundary, the superiority of itacitinib over placebo for both the Day 28 ORR and Day 180 NRM endpoints can be claimed at Interim Analysis 2.

Table 3: Schedule of Assessments

Visit Day Item	Screening -28 to -1	Treatment ^a												EOT ^d	Retreatment ^e	Follow-Up		
		D1	D7	D14	D21	D28	D35	D42	D49	D56 ^b	D100	D180	D365 ^c			Safety ^f	GVHD ^g	Survival ^h
Informed consent	X																	
I/E criteria	X	X																

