7.3.1. Primary Efficacy Analysis

7.3.1.1. Day 28 Overall Response Rate

The primary efficacy endpoint, ORR at Day 28 (ie, with either a CR, VGPR, or PR at Day 28 assessment or other response assessments within 3 days of Day 28, before start of new anti-GVHD therapy), will be analyzed using a stratified CMH test. Note that the EOT visit must be accounted for in the Day 28 ORR calculation, because when the EOT and Day 28 visits occur at the same time, per protocol, EOT will supersede the Day 28 visit. That is, if the EOT visit occurs when the Day 28 visit is planned, data from the EOT visit will be used in lieu of the Day 28 visit.

Responders ([CIBMTR 2009](#), [Harris et al 2016](#); refer to Protocol Appendix B):

- (CR) Complete response
- (VGPR) Very good partial response
- (PR) Partial response

Non-responders:

- (MR) Mixed response
- (PD) Progression of disease
- (NR) No response
- (NA) Not applicable
- Other
- Missing (primary reason)
 - Death prior to the Day 28 visit
 - Withdrawal from study prior to the Day 28 visit
 - Initiation of new anti-GVHD therapy prior to the Day 28 visit
 - Missing visit

Day 28 ORR will be summarized using descriptive statistics (N, %) by treatment group with 2-sided exact binomial 95% CIs. P-value, mean proportion difference, odds ratio, and 95% Wald confidence limits calculated from stratified CMH test will be also presented.

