7.4.1.1. Primary Analysis of Nonrelapse Mortality Rate at Month 6 (Day 180)

For the primary analysis, NRM will be analyzed using a stratified CMH test. Month 6 NRM will be summarized using descriptive statistics by treatment group with 2-sided exact binomial 95% CIs. P-value, mean proportion difference, odds ratio, and 95% Wald confidence limits calculated from stratified CMH test will also be presented.

Let $\hat{p}_{pbo,i}$ be the estimated proportion of evaluable subjects in the placebo group in stratum i who died due to causes other than malignancy relapse prior to or on Day 180 (ie, excluding those subjects who are either ongoing and have not reached Day 180, who withdrew from study prior to Day 180, or who died due to relapse) with corresponding variance estimator $\hat{V}(\hat{p}_{pbo,i})$. Let $\hat{p}_{trt,i}$ and $\hat{V}(\hat{p}_{trt,i})$ be the same for the itacitinib group in stratum i .

The overall estimate of treatment difference in Day 180 NRM between placebo and itacitinib is defined as the following:

$$w * [\hat{p}_{pbo,standard} - \hat{p}_{trt,standard}] + (1 - w) * [\hat{p}_{pbo,high} - \hat{p}_{trt,high}]$$

Its 95% CI is the above estimate of difference

$$\pm 1.96 * \text{sqrt} (w^2 * (\hat{V}(\hat{p}_{pbo,standard}) + \hat{V}(\hat{p}_{trt,standard})) + (1 - w)^2 * (\hat{V}(\hat{p}_{pbo,high}) + \hat{V}(\hat{p}_{trt,high})))$$

With weight w defined by inverse of variance in 2 baseline GVHD risk groups. That is:

$$w = \frac{1/[\hat{V}(\hat{p}_{pbo,standard}) + \hat{V}(\hat{p}_{trt,standard})]}{1/[\hat{V}(\hat{p}_{pbo,standard}) + \hat{V}(\hat{p}_{trt,standard})] + 1/[\hat{V}(\hat{p}_{pbo,high}) + \hat{V}(\hat{p}_{trt,high})]}$$

7.4.1.2. Sensitivity Analysis of Nonrelapse Mortality Rate at Month 6 (Day 180) Using Kaplan-Meier Approach

A sensitivity analysis will also be conducted where NRM at Day 180 will be estimated by 1 minus the survival probability at Day 180 using the KM estimator.

A stratified test statistic for NRM rate at Day 180 is proposed as:

$$TS_{Day180NRM} = \frac{\left[\sum_{j=1}^2 (\widehat{CDF}_{pbo,j}(t=D180) - \widehat{CDF}_{trt,j}(t=D180)) \right]^2}{\sum_{j=1}^2 Var(\widehat{CDF}_{pbo,j}(t=D180) - \widehat{CDF}_{trt,j}(t=D180))}$$

$$= \frac{\left[\sum_{j=1}^2 (\widehat{CDF}_{pbo,j}(t = D180) - \widehat{CDF}_{trt,j}(t = D180)) \right]^2}{\sum_{j=1}^2 (SE(\widehat{CDF}_{pbo,j}(t = D180))^2 + SE(\widehat{CDF}_{trt,j}(t = D180))^2)}$$

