[Table 2](#) lists efficacy boundary when information fraction (ie, the percentage of subjects) is 0.826 (360 subjects complete Day 28 or withdraw from the study) at Interim Analysis 2. If the test on ORR at Day 28 crosses the boundary, then the key secondary endpoint, 6-month NRM rate, will be tested using a separate boundary using the Bonferroni method for alpha-spending (ie, 0.0125 as compared with 1-sided p-value at both interim and final analyses). Note that [Table 2](#) will be re-derived when the observed information for ORR at Day 28 is not 0.826.

Therefore, efficacy analysis at Interim 2, assuming information fraction being 0.826 (ie, 360/436) will be conducted as follows:

- E1: Obtain CMH test statistic on ORR at Day 28 (chi-square test with degree of freedom 1),
- E2: CMH test statistic will be compared with the critical value in Column 7 of [Table 2](#) (Interim 2 chi-square test critical value),
- E3: If positive on ORR at Day 28, NRM rate at Day 180 will be tested using the Bonferroni method,
- E4: If neither efficacy nor futility on Day 28 ORR is crossed, study will continue.

Assuming that at the Interim Analysis 2 data cutoff date (Day 180 of the 240th randomized eligible subject) there are approximately 360 subjects based on estimation who have been randomized, then testing of Day 28 ORR will be conducted for subjects who have completed Day 28 or withdrawn from the study upon the cutoff date. This means that, by the Interim Analysis 2 data cutoff date, subjects who were ongoing but had not reached the Day 28 visit will be excluded for both the Day 28 ORR and Day 180 NRM analyses.

Analysis of NRM rate at Day 180 will use the same method as described in Section [7.4.1](#) for final analysis but using the Interim Analysis 2 cutoff data instead. The decision process is described in [Figure 4](#).

At the Interim Analysis 2 data cutoff date, if the total number of randomized subjects in the Interim 2 analysis set is different from the predicted number 360, the efficacy boundaries will be recalculated based on the actual observed information fraction at Interim Analysis 2.

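### Entry to the Interim 2 primary ORR test is set by visit completion and study status instead of elapsed time, so it can depend on outcome

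*SAP*

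**What the plan says.** SAP 5.3.2.1 builds the Interim 2 efficacy set from all randomised subjects but "excludes subjects who are ongoing at the clinical data cutoff date and have not finished the Day 28 visit". The set serves every efficacy analysis at that look.

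SAP 3.4.2 states the population positively: "Testing of Day 28 ORR will be conducted for subjects who have completed the Day 28 visit or withdrew from the study", by the cutoff. It then explains that the rule excludes "subjects who were ongoing but had not yet reached the Day 28 visit by the Interim Analysis 2 clinical data cutoff date", from both the ORR and the NRM analyses. SAP 9.1.2 repeats the explanation: "subjects who were ongoing but had not reached the Day 28 visit will be excluded". The SAP does not define "ongoing".

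On scoring, SAP 7.3.1.1 lists "Initiation of new anti-GVHD therapy prior to the Day 28 visit" and a missing visit as nonresponse, separately from death and study withdrawal. Protocol 9.4.1 says: "Subjects who are missing Day 28 aGVHD response assessment data will be considered to be nonresponders".

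On study status, Protocol 5.5 says: "The decision to discontinue study treatment will not constitute study completion". Protocol 5.5.2 says that a subject who permanently stops study drug is withdrawn from the study.

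SAP section 6 substitutes the interim efficacy set for the FAS if the study stops at an interim. SAP 5.3.2 gives the cutoff as 17 APR 2019; SAP Amendment 1 is dated 23 JUL 2019.

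**The concern.** Membership in a test that spends alpha should not depend on what happened to the subject. Here it can, in two ways.

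First, near the cutoff. Only ongoing subjects are removed. A subject randomised two weeks earlier who has already died or withdrawn stays in as a nonresponder; one randomised the same day and doing well is left out. This holds however the text is read.

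Second, further back. Day 28 is a treatment-period visit in Protocol Table 3. A subject who progresses on, say, Day 10 has an end-of-treatment visit and safety follow-up, then survival contacts under Protocol 6.5.3. SAP 4.1.5 maps the end-of-treatment assessment to Day 28 only if it falls within 3 days of that day. Such a subject can be alive in follow-up months later with no Day 28 visit and, under Protocol 5.5, still in the study. Read literally, 5.3.2.1 drops that subject and keeps the same failure who has died or withdrawn. A randomised subject who was never dosed and remains in the study is also dropped, because SAP 4.1.1 starts Day 1 at the first dose.

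At stake are both reported response rates, the information fraction and hence the boundary, and possibly the error rate of the primary test. The final all-randomised analysis would not correct this if the study stopped at Interim 2.

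**Working it through.** **Inputs.** ORR 56% vs 72% (SAP 3.3). Hwang-Shih-DeCani spending with parameter -4, one-sided 0.025, 436 planned and 360 illustrative subjects at Interim 2 (SAP 3.4.2, Table 2). Assumption: q, the share of nonresponders who are alive without a Day 28 visit and so dropped. The documents give no value for q.

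**Plan's own figures.** Alpha spent at information fraction t is 0.025(e^(4t) - 1)/(e^4 - 1). At t = 360/436 = 0.8257 this is 0.0122, so the boundary is 2.2503. Table 2 has 0.0122 and 2.249810; the gap comes from rounding t to 0.826. At 410/436 the boundary is 2.0622, as in Appendix D.

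**Formulas.** With n per arm and true rate p, the retained number is n[1 - q(1 - p)] and the observed ORR is p/[1 - q(1 - p)]. N is the sum of the retained numbers and t = N/436. Interim power is Φ(d/SE - boundary), where d is the observed difference and SE is unpooled and unstratified. A pooled null variance gives values up to about one point lower.

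**Example, q = 20% in both arms, n = 180.** Placebo keeps 180(1 - 0.2 × 0.44) = 164.2, with ORR 0.56/0.912 = 61.4%. Itacitinib keeps 180(1 - 0.2 × 0.28) = 169.9, with ORR 0.72/0.944 = 76.3%. N = 334, t = 0.766, alpha 0.0095, boundary 2.344. d = 0.149, SE = 0.0501, d/SE = 2.97. Power = Φ(2.97 - 2.34) = 73%.

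**Equal exclusion, 56% vs 72%**

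| q | ORR placebo / itacitinib | Difference (points) | Power, 180 per arm | Power, 218 per arm |
|---|---|---|---|---|
| 0 | 56.0 / 72.0 | 16.0 | 83% | 94% |
| 5% | 57.3 / 73.0 | 15.8 | 81% | 93% |
| 10% | 58.6 / 74.1 | 15.5 | 79% | 92% |
| 20% | 61.4 / 76.3 | 14.9 | 73% | 88% |

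The 218 column is the limit in which all 436 were randomised and past Day 28.

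**Null, 56% in both arms, 180 per arm**

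| q placebo / itacitinib | Spurious difference (points) | Shift in z | Alpha allotted | Chance of crossing |
|---|---|---|---|---|
| 10% / 10% | 0 | 0 | 1.05% | 1.05% |
| 10% / 20% | +2.8 | +0.53 | 0.97% | 3.5% |
| 15% / 30% | +4.6 | +0.85 | 0.87% | 6.3% |
| 30% / 15% | -4.6 | -0.85 | 0.87% | 0.06% |

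**Near-cutoff asymmetry.** The documents give neither the enrolment pace before the cutoff nor the timing of early events. At the plan's early withdrawal rate of up to 5%, every 20 subjects enrolled in the last four weeks would contribute about 20 × 0.05 = 1 such nonresponder.

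**The case against.** The strongest reply is that the SAP means a time rule. Sections 3.4.2 and 9.1.2 describe the excluded subjects as not yet at Day 28, which does not naturally fit someone months into follow-up. The NRM analysis points the same way: SAP 7.4.1.1 removes subjects "either ongoing and have not reached Day 180, who withdrew from study prior to Day 180", and SAP 7.4.1 explains the first group as alive and short of Day 180, which is elapsed time. The nonresponse categories for new therapy and missing visits would be largely empty at Interim 2 if those subjects had been removed. Under Protocol 5.5.2, early stoppers count as withdrawn and stay in the ORR set.

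Much of this stands: a reader might infer that early failures certainly drop out, and the documents do not establish that. They do not rule it out either. Section 5.3.2.1 is the set definition, and it asks whether the visit was finished. The scoring rules say how to classify a subject, not who is in the set. Protocol 5.5 and 5.5.2 conflict. Relying on 5.5.2 also has a price: SAP 7.4.1 leaves subjects who ended participation before Day 180 out of the NRM proportion, so living early stoppers would leave that test.

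A reader might also infer a large loss of power. The SAP calls its boundaries at 360 subjects a hypothetical illustration, and Appendix D tabulates Interim 2 sets of 410 to 435. To retain 410 with q = 20% would need 410/0.928 = 442 randomised; with q = 50%, 410/0.82 = 500. Against 436 planned, large exclusions look unlikely. This is not proof, because the number randomised at the cutoff is not given.

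Finally, a subject dropped at Interim 2 returns in the FAS if the study continues, so lost interim power is not lost study power.

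**Conclusion.** The point holds as a moderate defect of definition. The near-cutoff asymmetry follows from the text under any reading and is probably small. The loss of living early failures follows from the literal wording of SAP 5.3.2.1 and contradicts the plan's own nonresponder rules, but may not be intended.

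If the literal rule were applied equally in both arms, both ORRs would be overstated and the test would be conservative. At the plan's rates, interim power would fall by 2 to 10 points (180 per arm) or 1 to 6 points (218 per arm) for q between 5% and 20%.

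A reader might infer a general inflation of type I error. The documents do not support that: it needs more itacitinib than placebo nonresponders to be dropped, and the opposite imbalance lowers the error rate. All these sizes rest on assumed values of q.

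The reason to act is that the set feeds an alpha-spending primary test and replaces the FAS if the study stops. This SAP version postdates the cutoff, so an undocumented programming choice between the readings would be made after the data cut.

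**What to change.** Use one definition in SAP 3.4.2, 5.3.2.1 and 9.1.2: all randomised subjects whose Day 28 window, including the 3 extra days, had closed by 17 APR 2019, whatever their treatment or study status. Anchor it to randomisation so that never-dosed subjects are included. Day 28 is 27 days after the first dose, the window adds 3, and Protocol 6.1 allows up to 2 days between randomisation and first dose. The rule therefore becomes randomised at least 27 + 3 + 2 = 32 days before the cutoff.

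Within that set, count death, withdrawal, new anti-GVHD therapy or a missing Day 28 assessment as nonresponse. Exclude everyone randomised later, including those who have already died or withdrawn. Separately, reconcile Protocol 5.5 with 5.5.2 on whether stopping study drug means leaving the study, since SAP 7.4.1 also depends on it.

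The cost is wording only, with no new data. The downside is that a few recent subjects with early events leave the interim set; they remain in the FAS if the study continues.

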5.3.2.2. Interim 2 Safety Analysis Set

The Interim 2 safety analysis set contains all subjects who have been randomized and have received at least 1 dose of study drug as of the Interim 2 cutoff date. The Interim 2 Safety Analysis Set will be used for all planned safety analyses at Interim 2. All safety tables, figures, and listings will be presented by actual treatment group.

